11.0 STATISTICAL CONSIDERATIONS

11.1 Stopping Criteria

If at any point in trial enrollment, >2 out of the first 5 patients experience symptoms of G3 or greater toxicity that is probably or definitely attributable to and did not pre-date SBRT, the trial will be suspended. Symptoms that pre-dated SBRT will not be count towards stopping criteria (example: central thorax patients requiring oxygen prior to and after SBRT will not be scored as G3 toxicity, however a new O2 requirement after RT would count towards stopping criteria). If at any time a grade 5 toxicity (death) is observed that is probably or definitely attributable to treatment, accrual will be suspended and the event will be reviewed by the principal investigator. Since some patients accruing to the trial may have metastatic disease, it is anticipated that deaths unrelated to the trial may be observed. Death that is felt either due to disease progression or patient comorbidity will not result in trial suspension.

11.2 Sample Size

The primary endpoint of this study is to assess the feasibility of surface-guided, respiratory gated delivery of CT-guided stereotactic radiotherapy for upper abdomen and lower thorax malignancies by confirming that gated treatment can be delivered successfully in more than 75% of scheduled treatment fractions using a novel surface guidance system. A total of 10 evaluable patients (as defined in Section 5.2) will be included, with five treatment fractions each, for a total of $n = 50$ evaluable fractions. In order to assess the feasibility of the gating methodology on the novel surface guidance system, we conducted a one-sample reliability demonstration test based on the binomial distribution. The study will be powered based on an expected success rate of 95% and a minimum accepted rate of 75%. With 10 patients and 5 fractions per patient, 50 total fractions ($n=50$) would be assessed. In-patient correlation is anticipated, as surface-guided delivery is in part patient-surface dependent, with an anticipated value of 0.2. With a one-sided alpha of 0.25 and $n=50$ fractions across 10 unique patients, we would have a minimum of 92% power to detect feasibility of successful gated delivery.

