	
 2. Evaluate the compatibility of a standard-of-care respiratory gating system and the novel surface-guidance system for concomitant use. 3. Determine the minimum safe planning target volume and planning organ-at-risk volumes to be subsequently utilized with the novel surface guidance system. 4. Determine the local, in-field control rate at three months post-treatment. 5. Determine acute toxicity rates at three months post-treatment. 6. Identify patient and or treatment factors that maximize the potential efficacy of surface guided breath-hold respiratory gating.
Endpoints:	
Primary Endpoint: Percentage of scheduled treatment fractions delivered successfully using the surface guidance system. Success will be defined as delivery of a given treatment fraction in one on-table attempt, without requiring use of a secondary (backup) motion management system, or alternative treatment machine. Unsuccessful delivery of a fraction will be defined as multiple attempts for gating without reproducible positioning, breath-hold, and/or surface guidance feedback, such that the fraction is abandoned.
 
Exploratory Endpoints:
 
 1. Geometric agreement between breath-hold positioning as determined by a novel surface guidance system compared with standard of care concomitant breath-hold CBCT image sets, as evaluated by average symmetric surface distance (ASSD), modified Hausdorff distance (MHD), and Dice similarity coefficient measurements. 2. Qualitative evaluation of the compatibility of a standard-of-care respiratory gating system and the novel surface-guidance system for concomitant use. 3. Quantitative and qualitative measurement of minimum planning target volume (PTV) margins and planning organ-at-risk volumes to be subsequently utilized with the novel surface guidance system as determined through measurement evaluations in exploratory endpoint 1. 4. Local, in-field control rate at three months post-treatment will be determined as part of standard-of-care clinical evaluation by the treating physicians, using RECIST criteria. 5. Qualitative description of acute (within 90 days) Grade 3 or higher non-hematologic toxicity events related to radiation therapy at three months post-treatment. 6. Qualitative description of patient and treatment site factors, such as unique patient surface topography or skin tone, that

	might impact surface imaging tracking at the region of interest.

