11.5 Statistical Analysis Plan

Our principal objective in this trial will be to determine the feasibility of surface guided, respiratory gated delivery of CT-guided stereotactic adaptive radiotherapy (CT-STAR) in the abdomen and lower thorax using a novel surface-guidance system. Given that no prior data exists for thoracic or abdominal SBRT using this surface guidance system for respiratory gating, we will also report descriptive statistics for treatment adaptation, dosimetry, geometric and phase agreement between the novel surface guidance system and CBCT, acute toxicity, in-field control rates, and minimum acceptable PTV and PRV expansions for treatment planning. As a pilot study we will establish these baseline parameters.

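### Section 11.2 gives two feasibility criteria that disagree (above 75% observed is 38/50; the stated test at alpha 0.25 needs 41/50) and prints no pass mark

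*Combined protocol and SAP*

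**What the plan says.** The primary endpoint in the Protocol Summary is a percentage: "Percentage of scheduled treatment fractions delivered successfully using the surface guidance system". The Protocol Summary and Sections 2.1, 11.2 and 11.3 all express feasibility as confirming that "gated treatment can be delivered successfully in more than 75% of scheduled treatment fractions".

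Section 11.2 also sets up a formal test. It names a one-sample reliability demonstration test based on the binomial distribution, with "an expected success rate of 95% and a minimum accepted rate of 75" per cent. It plans ten patients with five fractions each, 50 in all, and an in-patient correlation "with an anticipated value of 0.2". It continues "With a one-sided alpha of 0.25" and concludes that "we would have a minimum of 92% power to detect feasibility of successful gated delivery". It gives no critical number of successful fractions.

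Section 11.5, the Statistical Analysis Plan, opens with "Our principal objective in this trial will be to determine the feasibility of surface guided, respiratory gated delivery" and goes on to descriptive statistics. It gives no test, confidence bound or pass mark for the primary endpoint.

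**The concern.** A test at alpha 0.25 against a null rate of 75% must ask for an observed rate some way above 75%. A rule that asks only for an observed rate above the null value succeeds about half the time when the null is true. The two statements in Section 11.2 therefore lead to different counts, and the plan does not say which one decides.

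Feasibility is the trial's primary result and will be reported as a yes or no. If the final count falls between the two marks, one part of the plan supports a claim of feasibility and another does not. With no count fixed in advance, a reader could not tell whether the rule was chosen after the result was known.

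**Working it through.** **Inputs (all from Section 11.2).** Null rate p0 = 0.75; expected rate p1 = 0.95; one-sided alpha 0.25; 10 patients with 5 fractions each; in-patient correlation 0.2; stated power at least 92%. The plan names no correlation model. I assume a beta-binomial and check others.

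**Formula.** For correlation r and true rate p, each patient's number of successes out of 5 is beta-binomial with parameters a = p(1−r)/r and b = (1−p)(1−r)/r. At r = 0.2, (1−r)/r = 4, so a = 3 and b = 1 under p0, and a = 3.8 and b = 0.2 under p1. The total out of 50 is the sum of ten independent patients, obtained exactly by convolution. Type I error is P(total ≥ c) at p0, and power is the same probability at p1.

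**The plan's own figure first.** The smallest c with type I error at or below 0.25 is 41, and its power is 99.5%. Deflating the sample by the design effect, 1 + 4 × 0.2 = 1.8, gives an effective n of 50/1.8 = 27.8. Exact tests at n = 27 (23 or more) and n = 28 (24 or more) have power 99.0% and 98.8%. The crudest normal approximation, using the null variance under both hypotheses, gives 96.1%. So 92% holds as a floor, but the printed inputs do not reproduce it. Values near 92% need a changed input: correlation 0.8 (43/50, power 92.0%), the patient as unit (9/10, type I error 24.4%, power 91.4%) or alpha 0.05 (45/50, type I error 3.4%, power 91.1%).

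**The two criteria as counts.** 37/50 = 74% and 38/50 = 76%, so an observed rate above 75% means at least 38.

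| Pass mark | Type I error, r = 0.2 | Power, r = 0.2 | Type I error, independent fractions |
|---|---|---|---|
| 38/50 | 51.9% | 99.96% | 51.1% |
| 39/50 | 42.3% | 99.90% | 38.2% |
| 40/50 | 32.9% | 99.77% | 26.2% |
| 41/50 | 24.2% | 99.48% | 16.4% |

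The step from 38 to 41 costs 99.96 − 99.48 = 0.48 points of power.

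**Sensitivity to the model.** The type I error of 38/50 lies between 51.1% and 52.6% for every beta-binomial correlation from 0 to 1. Under four cluster models with 0.2 as the correlation, it is 51.8% to 52.7% for 38/50. For 41/50 it is 21.8% to 24.4%, with power 99.2% to 99.9%.

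**Sensitivity to the correlation.** 41/50 keeps type I error within 0.25 for correlations from 0 to about 0.22 (24.7% at 0.22, 25.0% and just over the limit at 0.23). At 0.3 it is 26.7%, and 42/50 is needed (19.5%, power 98.1%).

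**Chance of landing on 38, 39 or 40 (r = 0.2).** At a true 75% this is 51.9% − 24.2% = 27.7%. By the same calculation it is 28.2% at 80%, 18.1% at 85%, 5.9% at 90% and 0.5% at 95%.

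**The case against.** The strongest reply is that 75% is the null value. Section 11.2 calls it the minimum accepted rate, names a binomial test and gives alpha. The wording about exceeding 75% then describes the hypothesis to be shown, and no sentence says that an observed 38/50 establishes feasibility. On that reading the 52% belongs to a rule the plan never adopts. The pass mark of 41/50 also follows from the stated inputs, whether fractions are treated as independent or as correlated at 0.2.

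Much of this stands. The 52% is conditional on applying the wording to the observed rate, and a statistician given Section 11.2 alone would probably arrive at 41/50. Two things remain. The endpoint is an observed percentage and the objective is repeated in four places without the test, so the observed-rate reading is open to anyone. And the count is printed nowhere, while Section 11.5 is silent.

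A second reply is that this is a ten-patient pilot and the contested counts are rare if the system performs as expected. That is correct at 95% (0.5%). But the test is there to guard against rates near 75%, where the chance is about 28%.

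A reader might infer more than the documents support:

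- That the trial actually runs at 52% type I error. It does so only if the wording is used as the decision rule.
- That the trial is underpowered or the 92% is wrong. It is stated as a minimum, and power at the printed inputs is about 99%.
- That 0.25 is a misprint or unsuitable for a pilot. Nothing in the documents shows this.

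**Conclusion.** The point holds as an inconsistency with a missing pass mark. Section 11.2 words feasibility in a way that admits 38/50 and specifies a test that needs 41/50. If the wording is applied to the observed rate, type I error is about 52%, roughly double the stated 25%, at any correlation. If the test governs, 41/50 is the mark, with type I error 24.2% and power 99.5%, but the reader has to derive it.

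The 41/50 mark rests on alpha 0.25 being intended, on 50 scheduled fractions, and on a correlation no higher than about 0.22. The 52% rests on almost nothing beyond the observed-rate reading.

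It should be fixed before results are known, because it determines how the primary conclusion is reached. It gives no reason to change enrolment. The unreproduced 92% is a note only.

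**What to change.** In Section 11.2, say that 75% is the null rate, confirm the intended alpha, and print the pass mark, the correlation model, the attained type I error and the power. Carry the pass mark into Sections 11.3 and 11.5. If 0.25 is confirmed, suitable text would be:

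> The null success rate is 75%. Feasibility will be concluded if at least 41 of the 50 scheduled fractions succeed. With in-patient correlation 0.2 (beta-binomial), type I error is about 24% at a true rate of 75% and power is about 99% at 95%.

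If another alpha was intended, give it with its own figures; at 0.05, for example, they are 45/50, 3.4% and 91.1%.

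Three additions belong with it:

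- State how scheduled fractions that are not delivered count. Section 5.2 makes any irradiated patient evaluable and Section 5.5 allows treatment to stop early, so fewer than 50 fractions may be delivered.
- Note that 41/50 exceeds alpha 0.25 if the correlation is above about 0.22 (26.7% at 0.3, where 42/50 is needed).
- Replace the 92% with the attained power, or state the correlation or unit of analysis behind that bound.

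The cost is a paragraph in Section 11.2 and a sentence each in 11.3 and 11.5. The pass mark becomes stricter than 38/50, at a loss of about 0.5 points of power. No patients, visits or data are added.

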11.3 Primary Objective

Demonstrate that surface guided, respiratory gated delivery of CT-guided stereotactic adaptive radiotherapy (CT-STAR) is feasible in the abdomen and lower thorax by confirming that gated treatment can be delivered successfully in more than 75% of scheduled treatment fractions using a novel surface guidance system. Success will be defined as delivery of a given treatment fraction in one on-table attempt, without requiring use of a secondary (backup) motion management system, or alternative treatment machine. Unsuccessful delivery of a fraction will be defined as multiple attempts for gating without reproducible positioning, breath-hold, and/or surface guidance feedback, such that the fraction is abandoned.

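### The plan anticipates a within-patient correlation of 0.2 but writes no primary analysis that allows for it; the only named test is a binomial on 50 fractions

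*Combined protocol and SAP*

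**What the plan says.** Section 11.2 (Sample Size) is the only place that names a method for the primary endpoint: "we conducted a one-sample reliability demonstration test based on the binomial distribution". The planning rates follow: "The study will be powered based on an expected success rate of 95% and a minimum accepted rate of 75" per cent. The data are 10 patients with five fractions each, 50 in all.

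The same paragraph says that fractions from one patient are related: "In-patient correlation is anticipated, as surface-guided delivery is in part patient-surface dependent, with an anticipated value of 0.2". For these 50 fractions it sets alpha at 0.25, one-sided, and gives the resulting power: "we would have a minimum of 92% power to detect feasibility of successful gated delivery". It does not say how the 0.2 enters that calculation.

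Section 11.3 (Primary Objective) repeats the target of "confirming that gated treatment can be delivered successfully in more than 75% of scheduled treatment fractions" and defines a successful fraction. It gives no test, pass mark or interval.

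Section 11.5 (Statistical Analysis Plan) restates the feasibility aim and continues: "we will also report descriptive statistics for treatment adaptation, dosimetry, geometric and phase agreement", followed by toxicity, control rates and margins. The primary success rate is not in that list, and neither a test nor a way of handling repeated fractions per patient is given.

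**The concern.** A one-sample binomial test with n = 50 takes the fractions to be independent. Section 11.2 gives a reason why they are not: gating depends partly on the patient's surface, so failures will tend to fall in the same patients. With only ten patients, one unsuitable surface could produce up to five of the failures.

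An analyst who looks for the primary analysis finds only the binomial in Section 11.2. Applied as it stands to 50 fractions, it would overstate the precision of the one quantity that the trial is designed to estimate. If the method is instead chosen once the counts are known, the feasibility conclusion is open to the criticism that the method was picked to suit the result.

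**Working it through.** **Inputs (Section 11.2).** Minimum rate p0 = 0.75; expected rate p1 = 0.95; 10 patients × 5 fractions = 50; correlation ρ = 0.2; one-sided alpha 0.25; stated power at least 92%.

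**Design effect.** 1 + (5 − 1) × 0.2 = 1.8. Effective n = 50/1.8 = 27.8. A standard error computed on 50 independent fractions is too small by a factor of √1.8 = 1.34.

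**The plan's 92%.** No formula is given, so several were tried at alpha 0.25.

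- Independent fractions, exact binomial (pass at 41/50): power 0.9998.
- Independent fractions, Wald test on the logit scale, n = 50: 0.985.
- Correlation-adjusted, Wald test on the logit scale, n = 27.8: logit 0.95 − logit 0.75 = 2.944 − 1.099 = 1.846; √(27.8 × 0.95 × 0.05) = 1.149; Φ(1.846 × 1.149 − 0.674) = Φ(1.446) = 0.926.
- Other correlation-adjusted variants: exact binomial on n = 27 or 28, 0.990 or 0.988; normal approximation, 0.961 to above 0.999; beta-binomial, 0.995.

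One adjusted variant reproduces the stated figure, and no independent variant tried does. This suggests that the correlation was used at the design stage but does not prove it. A beta-binomial at alpha 0.05 (pass at 45/50) also comes close, at 0.911, but 0.05 is not the stated alpha.

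**Model for the check.** Each patient's success probability follows a beta distribution with parameters p(1 − ρ)/ρ and (1 − p)(1 − ρ)/ρ. At p = 0.75 and ρ = 0.2 these are 3 and 1. The total is the sum of ten independent beta-binomial counts of five.

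**p-values against 75%.**

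| Successes | Binomial, n = 50 | Beta-binomial, ρ = 0.2 |
|---|---|---|
| 40/50 | 0.262 | 0.329 |
| 41/50 | 0.164 | 0.242 |
| 42/50 | 0.092 | 0.167 |
| 43/50 | 0.045 | 0.107 |

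Under both models 40/50 fails and 41/50 passes at 0.25. Two other models for correlated binary data give 0.242 and 0.244 at 41/50, so the result does not hang on the beta-binomial form.

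**True error of the 41/50 rule by correlation.**

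| ρ | True one-sided error |
|---|---|
| 0.1 | 0.208 |
| 0.2 | 0.242 |
| 0.3 | 0.267 |
| 0.5 | 0.304 |

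At 0.3 or 0.5 the beta-binomial pass mark would be 42/50 (tails 0.195 and 0.238).

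**Intervals.** With ρ = 0.2, a 95% exact binomial interval on n = 50 covers 88.5% to 90.4% for true rates of 75% to 90%, and 95.3% at a true rate of 95%. At 41/50 the 75% one-sided lower limit is 76.9% on n = 50 and 74.5% on effective n = 27.8.

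**The case against.** The best defence is that the binomial sentence stands under Sample Size, is in the past tense, and describes a design calculation. A reader might infer that the plan treats the 50 fractions as independent. The documents do not say so, and the stated power speaks against it: independence at alpha 0.25 gives 98.5% or more, while one adjusted calculation gives 92.6%. That stands. The gap is an analysis that has not been written, and Section 11.5 promises no p-value or interval that could be called wrong today.

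A reader might also infer that ignoring the correlation would reverse the conclusion. At the plan's own alpha and correlation it would not, since both tests pass at 41/50. Reversals appear at 43/50 and 44/50 only if a 95% one-sided bound is required, and the documents set no such bound. At the plan's 75% one-sided level, 43/50 gives lower limits of 81.2% (n = 50) and 78.8% (effective n), and 44/50 gives 83.3% and 81.0%; all clear 75%. For the same reason, a pass mark of 45/50 at one-sided 0.05 cannot be brought in as a clustering correction, because it would replace the protocol's alpha. Whether 0.25 is the intended alpha is a separate question for the sponsor.

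Finally, this is a ten-patient pilot, and at the expected 95% success rate the plain exact interval keeps its nominal coverage. That lowers the severity. It does not remove the need to state the analysis, because the trial must also be readable if the success rate falls short of 95%.

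**Conclusion.** The point holds as an omission with a measurable consequence. The plan recognises a correlation of 0.2 but writes no primary analysis that uses it, and the only method on the page would give error bars that are too narrow. At 41/50 the p-value would be 0.164 instead of 0.242. Nominal 95% coverage would be about 88-90% at true rates of 75-90%, with no loss at 95%.

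The pass/fail decision at one-sided 0.25 and correlation 0.2 is unaffected, but the margin is thin: 0.242 against 0.25, exceeded at a correlation of 0.3. The 0.2 is itself only anticipated, and Section 11.5 acknowledges that there are no prior data for this use.

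The figures assume five fractions in each of ten patients, a common correlation, and the beta-binomial model. The inference that the design calculation used the correlation rests on one matching formula. Severity is moderate.

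**What to change.** Add to Section 11.5:

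- **Primary test.** The beta-binomial tail probability for 10 patients × 5 fractions with correlation 0.2, against 75%, at the protocol's stated alpha. At one-sided 0.25 the pass mark is 41/50. Repeat at correlations of 0.3 and 0.5 as sensitivity analyses.
- **Estimate.** The success rate with an interval that allows for clustering by patient, for example an exact interval on effective n = fractions/(1 + 4 × correlation).
- **Listing.** The ten per-patient success counts, so that a reader can see whether failures are concentrated in a few patients.
- **Precedence.** A sentence saying that the test governs the decision.

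The last item is needed because the effective-n interval is somewhat conservative (coverage 96-99% at correlation 0.2) and can disagree with the test at the margin. At 41/50 the test passes at 0.242, while the 75% one-sided lower limit is 74.5%.

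The cost is SAP wording and a few lines of code, with no extra patients or data. The reported interval becomes about one-third wider (√1.8 = 1.34). The text should be settled before the fraction outcomes are analysed.

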11.3 Primary Objective

Demonstrate that surface guided, respiratory gated delivery of CT-guided stereotactic adaptive radiotherapy (CT-STAR) is feasible in the abdomen and lower thorax by confirming that gated treatment can be delivered successfully in more than 75% of scheduled treatment fractions using a novel surface guidance system. Success will be defined as delivery of a given treatment fraction in one on-table attempt, without requiring use of a secondary (backup) motion management system, or alternative treatment machine. Unsuccessful delivery of a fraction will be defined as multiple attempts for gating without reproducible positioning, breath-hold, and/or surface guidance feedback, such that the fraction is abandoned.

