2.2 Exploratory Objectives

1. Determine geometric agreement between breath-hold positioning as determined by a novel surface guidance system vs. concomitant breath-hold CBCT image sets.
2. Evaluate the compatibility of a standard-of-care respiratory gating system and the novel surface-guidance system for concomitant use.
3. Determine the minimum safe planning target volume and planning organ-at-risk volumes to be subsequently utilized with the novel surface guidance system.
4. Determine the local, in-field control rate at three months post-treatment.
5. Determine acute toxicity rates at three months post-treatment.
6. Identify patient and or treatment factors that maximize the potential efficacy of surface guided breath-hold respiratory gating, such as differences in surface topography and skin tone.

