5.1.8 Surface-Guided Gated Delivery

At time of CT and CBCT simulation, a baseline reference surface region of interest will be determined. The region of interest (ROI) will be selected on an individual basis for the most sensitivity to detect respiratory motion. At time of first treatment, the patient will be set up to marks and the reference surface. Breath-hold CBCT daily alignment image will be acquired and a new reference surface ROI will be established based on the daily anatomy. The reference surface will be monitored using the Identify system and a respiratory trace will be generated and displayed to the treatment team for breath-hold respiratory gating of treatment delivery. A visual feedback system will be displayed to the patient to aid in respiratory coaching for breath-hold. After treatment alignment and optional adaptation, a repeat breath-hold CBCT will be obtained to evaluate for any patient motion. Shifts can be applied as needed prior to initiation of delivery. CBCT can be repeated in the breath-hold position at set time points, e.g., after each arc in VMAT plans, and at the end of treatment delivery. A recommended maximum of 10 images will be taken per fraction. This will be used for intrafraction patient monitoring as well as subsequent evaluation of concordance between geometric patient position as identified by the Identify system vs. CBCT.

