5.2 Evaluability Guidelines

All patients who receive any radiation therapy are evaluable for the primary objective (feasibility of delivering CT-guided SBRT with surface-guidance for gated delivery).

Patients who receive at least one fraction of radiation therapy are evaluable for the

exploratory objectives relating to tumor response/control rate and toxicity.

Success will be defined as delivery of a given treatment fraction in one on-table attempt, without requiring use of a secondary (backup) motion management system, or alternative treatment machine. Unsuccessful delivery of a fraction will be defined as multiple attempts for gating without reproducible positioning, breath-hold, and/or surface guidance feedback, such that the fraction is abandoned.

Should respiratory gating using the Identify optical surface guidance system not be feasible for any given fraction or patient, the treatment fraction will be delivered using an alternative, backup motion management device and/or an alternative linear accelerator as per standard-of-care therapy.

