11.4 Exploratory Objectives

- Determine geometric agreement between breath-hold positions as determined by a novel surface guidance system vs. concomitant breath-hold CBCT image sets. Geometric agreement will be evaluated by average symmetric surface distance (ASSD), modified Hausdorff distance (MHD), and Dice similarity coefficient measurements.
- Evaluate the compatibility of a standard-of-care respiratory gating system and the novel surface-guidance system for concomitant use. This will be evaluated qualitatively.
- Determine the minimum safe planning target volume (PTV) and planning organ-at-risk volumes (PRV) to be subsequently utilized with the novel surface guidance system. This will be determined through measurement evaluations in the first exploratory endpoint.
- Determine the local, in-field control rate at three months post-treatment. This will be determined by the treating physicians using RECIST criteria.
- Determine acute toxicity rates at three months post-treatment. This will be assessed by a qualitative description of grade 3 or higher non-hematologic toxicity events related to radiation therapy at three months post-treatment.
- Identify patient and or treatment factors that maximize the potential efficacy of surface guided breath-hold respiratory gating. These include factors such as surface topography features as well as skin tone. This will be evaluated qualitatively.

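### Does the success rule leave unscored a surface-guided fraction that needed repeat gating tries, or one on which a second gating system also ran?

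*Combined protocol and SAP*

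**What the plan says.** The Protocol Summary gives the primary endpoint as "Percentage of scheduled treatment fractions delivered successfully using the surface guidance system". The same success sentence stands in the Protocol Summary and in sections 2.1, 5.2 and 11.3: the fraction must be delivered "in one on-table attempt, without requiring use of a secondary (backup) motion management system" or a different machine. A companion sentence describes an unsuccessful fraction as one with several gating attempts that could not be made reproducible, so that the fraction was given up. Section 5.2 adds that when gating with Identify is not feasible, the fraction is "delivered using an alternative, backup motion management device and/or an alternative linear accelerator as per standard-of-care therapy".

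Section 2.2 lists a second exploratory objective: "Evaluate the compatibility of a standard-of-care respiratory gating system and the novel surface-guidance system for concomitant use". Section 11.4 repeats it and assigns a qualitative assessment only.

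Section 5.1.8 sets out delivery. "The reference surface will be monitored using the Identify system and a respiratory trace will be generated" and shown to the team for breath-hold gating. A further breath-hold CBCT follows alignment and any adaptation, and "Shifts can be applied as needed prior to initiation of delivery". CBCT may be repeated during delivery. Section 1.6 describes treatment over a number of successive breath-holds. Section 5.1.8 mentions no second gating system.

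**The concern.** Two kinds of delivered fraction seem to fall between the success and failure sentences.

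- **Repeat gating tries.** Success speaks of an on-table attempt, failure of attempts at gating, and neither is defined. A fraction delivered under surface guidance after several tries in one session was not given up, so it is not a failure as described. It is a success if an attempt means a session, and not if it means a try.
- **Two systems running.** If a standard-of-care gating system runs beside Identify for objective 2, one may ask whether its presence disqualifies the fraction, particularly since the fallback in section 5.2 is also standard of care.

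This is the trial's only endpoint with a pass mark, and it rests on 50 fractions. If the scoring of a sizeable group of fractions were really open, it could be settled after the counts were known. For example, with 45 fractions delivered under surface guidance, 8 of them after repeat tries, one count gives 45/50 = 90% and the other 37/50 = 74%, on opposite sides of the mark.

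**Working it through.** **Inputs.** From section 11.2: 10 patients × 5 fractions = 50; minimum accepted rate 75%; expected rate 95%; in-patient correlation 0.2; one-sided alpha 0.25; stated power at least 92%. The share r of delivered fractions that need repeat tries and the number k of fractions with both systems running are not in the documents. They are assumed below and shown over ranges.

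**Criterion.** More than 75% of 50 means X > 37.5, so X ≥ 38 (38/50 = 76%; 37/50 = 74%).

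**The plan's own power figure.** Correlation is modelled with a beta-binomial: each patient's rate is Beta(a, b), with a = p(1 − 0.2)/0.2 = 4p and b = 4(1 − p), summed over 10 patients. At p = 0.75 the smallest cutoff with alpha no more than 0.25 is 41 of 50 (alpha 0.242), and power at p = 0.95 is 0.995. That does not reproduce 92%, but it is consistent with 92% as a floor. The figure has no bearing on how fractions are scored.

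**Size of the repeat-try question.** Under the session reading p = 0.95. Under the per-try reading p = 0.95(1 − r). The chance of X ≥ 38 is:

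| r (assumed) | p per try | independent | correlation 0.2 |
|---|---|---|---|
| 0 (session reading) | 0.950 | >99.9% | >99.9% |
| 5% | 0.9025 | 99.9% | 98.9% |
| 10% | 0.855 | 97.7% | 93.1% |
| 15% | 0.8075 | 84.9% | 78.5% |
| 20% | 0.760 | 57.7% | 56.8% |
| 25% | 0.7125 | 28.4% | 34.5% |

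The expected per-try rate falls to 75% at r = 1 − 0.75/0.95 = 21%. At the expected 47 or 48 deliveries, 10 or 11 fractions would have to be rescored to reach 37.

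**Which reading the text supports: repeat tries.**

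1. The success sentence attaches its attempt to the treatment table; the failure sentence attaches its attempts to gating. The different wording suggests different units.
2. Failure needs repeated gating attempts and loss of the fraction. Repeated attempts would not need that further condition if they were already disqualifying.
3. Sections 1.6 and 5.1.8 make several breath-holds, repeat CBCT and shifts part of an ordinary session. Counting each as an attempt would make routine delivery a non-success.

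All three favour attempt = session.

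**Which reading the text supports: two systems.**

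1. The rule turns on a second system being required and labels it a backup. A reading under which any use disqualifies has to delete both words.
2. Section 5.2 brings the backup in only when Identify gating is not feasible, and as an alternative to it. A device running alongside while Identify gates the beam is neither.
3. The any-use reading gives P(Bin(50 − k, 0.95) ≥ 38): 99.8% at k = 5, 67.7% at k = 10 and zero from k = 13, where at most 37 fractions can count. The arithmetic is right, but it prices a reading the wording does not support.
4. In the opposite direction, suppose surface guidance alone succeeds in 70% of fractions and the second system carries 20 fractions that are all scored as successes. Then P(20 + Bin(30, 0.70) ≥ 38) = 92%. But a carried fraction required the second system, so the rule already excludes it.

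**The case for a change.** The best case for a change is that this is the one endpoint with a threshold, that its key word is undefined, and that a single line would settle it at almost no cost. The exposure is also larger if the result is judged by the test in section 11.2 rather than by the point estimate: at a cutoff of 41 of 50, with correlation 0.2, the per-try reading gives 93.5% at r = 5%, 76% at r = 10% and 51% at r = 15%. Finally, objective 2 names concomitant use, yet section 5.1.8 describes no procedure that would produce it.

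Part of this stands. Attempt is undefined, a definition would be tidy, and the data source for objective 2 is not described. But objective 2 is exploratory and qualitative, so that gap does not reach the primary rate. The large effects all depend on values of r or k that the documents do not supply, combined with readings the wording disfavours. Nor can the per-try count inflate a claim of feasibility, since it can only be equal to or lower than the session count. One narrow case remains: both systems ran, and it cannot be told whether the second was needed. That is a judgement about an individual fraction, and a general definition would not remove it.

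**Conclusion.** No change is needed. This is missing detail that an analyst fills sensibly from the surrounding text. An attempt is one session on the table, and a standard-of-care system that only runs alongside does not disqualify a fraction that surface guidance gated. Fractions moved to the backup or to another machine are plainly not successes. With those readings the primary rate is computable as written, the criterion is 38 or more of 50, and at the planned 95% it is met with probability over 99.9%, with or without the correlation of 0.2.

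The conclusion rests on the study team applying these plain readings. If each try were counted instead, the chance would still be about 99% or more at an assumed repeat-try share of 5%, and would fall to about 57% at 20%; the documents give no basis for choosing a share. Stating the definition would record what the text already favours, and a second version of the primary rate or extra per-fraction items would be a matter of preference in a 10-patient pilot.
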